1. INTRODUCTION

The following Statistical Analysis Plan (SAP) was written and approved prior to the study enrollment. The text in this SAP reflects the analysis methods planned as of the date of the SAP. It includes more details to the analyses mentioned in the protocol and may be amended to reflect any additional analyses planned prior to unblinding the data.

2. STUDY OBJECTIVES

2.1 Primary Objective

To investigate the effects of the 3M Oral Rinse relative to the placebo vehicle control on plaque and gingivitis levels, at 6 months, based on the Modified Quigley-Hein Plaque Index (PI) and the Löe-Silness Gingival Index (GI) scores.

2.2 Secondary Objectives

- To investigate the effects of the 3M Oral Rinse vs. Placebo Vehicle Control on plaque and gingivitis, at 3 months, based on the Modified Quigley-Hein Plaque Index (PI) and the Löe-Silness Gingival Index (GI) scores.
- To investigate the effects of the 3M Oral Rinse vs. Placebo Vehicle Control on Eastman Interdental Bleeding Index (BI) scores at 3 and 6 months
- To investigate the relative efficacy, using pairwise comparisons, of the four treatment groups, namely 3M Oral rinse, vehicle control, PerioShield (predicate) and water control, with respect to the PI and GI scores at 6 months.
- To assess the safety of the 3M oral rinse by tracking abnormal changes to soft and hard tissues, reported side effects and adverse events during the study.

3. INVESTIGATIONAL PLAN

3.1 Study Design

This is a prospective, single site, randomized, parallel, blinded clinical trial. Subjects will be randomly assigned to one of four treatment groups. The treatment groups are presented below:

Treatment Groups

Treatment Code	Study Product	Description
A	3M Oral Rinse	The volume of 15 mL will be swished for 30 seconds followed by expectoration, twice a day (morning and evening), after brushing teeth, for the 6-month duration of the study.
B	3M Vehicle Control	The volume of 15 mL will be swished for 30 seconds followed by expectoration, twice a day (morning and evening), after brushing teeth, for the 6-month duration of the study.
C	PerioShield (Predicate)	PerioShield™ Oral Health Rinse (0.2% delmopinol hydrochloride) is marketed in the US and will be purchased for use in the study. The subjects will follow the product instruction for use using 10 mL for 30 seconds followed by expectoration, twice a day (morning and evening), after brushing teeth, for the 6-month duration of the study.
D	Water	The water control will be purchased sterile water. The volume of 15 mL will be swished for 30 seconds followed by expectoration, twice a day (morning and evening), after brushing teeth, for the 6-month duration of the study.

3.2 Randomization

The treatment groups consisting of four different oral rinses will be assigned to the letter labels A, B, C, D.

The randomization was created by a biostatistician who will not be involved in the analysis of the study data, keeping the study biostatistician blinded to the randomization schedule. The randomization schedule created treatment assignments for 216 subjects, 16 extra over the protocol specified sample size to account for contingencies. The randomization ratio was 1:1:1:1 among the four treatment groups.

Details of the randomization scheme followed, and the protocol deviations related to randomization errors will be documented in the final study report.

3.3 Blinding and Blinding Assessment

Before data lock and final study data analysis, the biostatistician will remain blinded to treatment assignment. The final data review and data classification meeting will be conducted before data lock and statistical programming will occur using dummy treatment assignments.

The Principal Investigator and clinical examiners will be blinded to the treatment products. No clinical examiners will see the allocated rinse assigned per the randomization schedule. Due to the rinse packaging differences and to maintain the blind, all study products will be placed in a non-transparent container. Subjects will be told not to open the container until they return to their home and to bring study supplies back to their next scheduled appointment in the same container. Only the study coordinator at the site will know the randomization assignment.

Each subject will be asked to indicate to what treatment he or she thinks they have been assigned. This assessment will be done immediately after the first dose and at the end-of-study visit. The subject will indicate if he or she thinks the treatment assigned is (a) the new 3M Oral Rinse, (b) one of the control rinses, or (c) does not know or cannot make an educated guess. The responses to the blinding assessment questionnaire at both time points will be summarized by the randomized treatment group.

4. Efficacy Endpoints

4.1 Löe-Silness Gingival Index (GI)

0=	Absence of inflammation.
1=	Mild inflammation: slight change in color and little change in texture.
2=	Moderate inflammation: moderate glazing, redness, edema, hypertrophy. Tendency to bleed upon probing.
3=	Severe inflammation: marked redness and hypertrophy. Tendency to spontaneous bleeding.

The gingival surface surrounding each tooth (all natural teeth) will be scored on six surfaces: 1) mesio-facial; 2) mid-facial; 3) disto-facial; 4) mesio-lingual; 5) mid-lingual; and 6) disto-lingual. Third molars and those teeth with cervical restorations or prosthetic crowns will be excluded from the scoring procedure. The GI score of the individual will be obtained by adding the scores of all surfaces and dividing by the number of surfaces examined.

4.2 Modified Quigley-Hein Plaque Index (PI)

0=	No plaque.
1=	Separate flecks of plaque at the cervical margin of the tooth.
2=	A thin, continuous band of plaque (up to one mm) at the cervical margin of the tooth.
3=	A band of plaque wider than 1 mm but covering less than 1/3 of the crown of the tooth.
4=	Plaque covering at least 1/3, but less than 2/3 of the crown of the tooth.
5=	Plaque covering 2/3 or more of the crown of the tooth.

Prior to examination, a plaque disclosing solution will be applied to all surfaces of teeth. Each tooth is scored for supragingival plaque on six surfaces: 1) mesio-facial; 2) midfacial; 3) disto-facial; 4) mesio-lingual; 5) mid-lingual; and 6) disto-lingual. Third molars and those teeth with cervical restorations or prosthetic crowns will be excluded from the scoring procedure. The PI score of the individual will be obtained by adding the scores of all surfaces and dividing by the number of surfaces examined.

4.3 Eastman Interdental Bleeding index (BI)

0=	Absence of bleeding.
1=	Presence of bleeding

The interdental cleaner is inserted between two teeth from the facial aspect, depressing the interdental tissues 1 to 2 mm. This is repeated four times and the presence or absence of bleeding within 15 seconds is recorded. The absence or presence of bleeding will be recorded for each examined site (between two teeth), and a score will be calculated as the number of bleeding sites out of the number of examined sites for each evaluation on a subject.

5. ANALYSIS POPULATIONS

5.1 Safety Population

All subjects will be included in the safety analyses.

5.2 Intent-To-Treat Population

The intent-to-treat (ITT) data set will be the primary efficacy data set and will include all subjects randomized to a treatment group. Subjects will be analyzed in the group to which they were randomly assigned. Subjects with missing post-baseline PI and/or GI data will be included in the ITT analysis using appropriate input data sets and imputation methods. The Expectation-Maximization (EM) algorithm will be used, and this procedure assumes the data will be multivariate normal and missing at random. If these assumptions prove to be violated, other methods will be considered.

5.3 Per-Protocol Population

A second per-protocol (PP) data set will be defined excluding any subjects with major deviations or lack of compliance with taking their assigned study treatment. The PP dataset will be used only for the primary efficacy analysis (3M oral rinse vs. vehicle control) and the secondary efficacy analysis with all four treatment groups.

The following major protocol deviations will lead to exclusion from the per protocol data set:

- (1) Subject who is missing either one or both primary endpoints of GI and PI values at 6 months
- (2) Subject who did not meet the inclusion criteria of baseline Gingival Index (GI) score of ≥ 1.0 and a baseline Plaque index (PI) score of ≥ 1.5 .
- (3) Subject with $< 80\%$ of planned dose (or alternatively $>20\%$ of no rinsing).
- (4) Subject with ≥ 3 consecutive days of no rinsing within 4 weeks prior to PI and GI assessments.
- (5) Subject who indicated antibiotics, anti-inflammatory, anticoagulants, or immunosuppressant drug use, regardless of dose, within 6 weeks prior to PI and GI assessments.

All deviations not captured above that will result in exclusion from the PP analysis will be defined and justified in a blinded fashion. In addition, documentation will be made of these data classification decisions prior to data lock.

6. GENERAL STATISTICAL CONSIDERATIONS

Means and standard deviations will be calculated for all clinical measurements and assessments. Categorical variables will be summarized in frequency distributions. Analysis of variance (ANOVA) or (ANCOVA) will be used to test for treatment group differences between the subject groups over the visits. When appropriate, alternative statistical methods such as normalizing transformations or nonparametric tests may be used to analyze the data.

GI, PI, and BI scores will be calculated as the average tooth score across all measures and teeth surfaces as one score per patient, per visit. For example, a patient with 28 evaluable teeth will have 168 data points (6 per tooth) averaged per tooth and then averaged over all teeth to produce one score per patient per visit. The subject indices computed will range between 0-3 (GI) or 0-5 (PI) or 0-1 (BI).

All statistical analyses will be performed using SAS version 9.4 or above (SAS Institute, Cary, NC) or another statistical software package. Any changes to the methods proposed in this SAP will be documented in the “Changes to Planned Analyses” section of the final clinical study report.

6.1 Determination of Sample Size

The sample size was estimated based on GI and PI scores from preliminary clinical study data and the literature. It is estimated that 34 subjects per group will provide 90% power to detect a difference of 0.40 (standard deviation of 0.5) in the GI and PI scores using a 1-sided 0.025 alpha level. To account for possible dropouts, a sample size of 50 subjects per group will be recruited.

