8. EFFICACY ANALYSIS

8.1 Primary Efficacy Analysis (3M Oral Rinse vs. Vehicle Control)

Performance of the 3M Oral Rinse will be assessed based on two primary endpoints. Statistical analysis will be performed on the PI and GI scores at 6-months using an ANCOVA with treatment as the factor and baseline score as a covariate. The success criterion for the study will be based on the single comparison between the 3M Oral Rinse group and the vehicle control group. The primary efficacy analysis will exclude data from the other two treatment groups, namely, the PerioShield (predicate) and the water control groups.

Significance of the overall treatment effect will be assessed by the p-value associated with the F-test statistic for the treatment group. The level of significance will be two-sided alpha of 0.05. The main null hypothesis of interest to support that 3M Oral Rinse reduces plaque and gingivitis is as follows:

$$H_0: \mu_{3M \text{ Oral Rinse}} \geq \mu_{\text{Vehicle}} \text{ versus } H_A: \mu_{3M \text{ Oral Rinse}} < \mu_{\text{Vehicle}}$$

Both primary endpoint comparisons will be based on the intent-to-treat (ITT) data set. The study will be considered successful if both primary endpoints are met.

In the event of a significant demographic or baseline variable, the primary efficacy ANCOVA model will be expanded to include this significant variable as a covariate or factor in the model. Statistical models with interaction terms or subgroup analyses will be explored if appropriate to help further understand the treatment effect.

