
Study Duration
	
The duration of subject involvement is approximately 6 months.
 
Study duration from the time of first subject enrolled until last subject completed is expected to be approximately 12-15 months.

Sample Size
	
The sample size was estimated based on GI and PI scores from preliminary clinical study data and the literature. It is estimated that 34 subjects per group will provide 90% power to detect a difference of 0.40 (standard deviation (SD) of 0.5) in the GI and PI scores using a 1-sided 0.025 alpha level. To account for possible dropouts, a sample size of 50 subjects per group will be recruited.

Screening Inclusion criteria:	Subjects to whom these criteria apply will be entered into the 7-day washout 
• Able to understand and willing to sign the Informed Consent• In good general health ages 18 and older• Have at least 20 natural teeth, including at least one molar and one premolar in each quadrant but excluding the third molars• Willing to return to the study facility for scheduled study visits and recalls• Agree not to use other oral hygiene products (non-study toothpaste, dental floss, mouth rinse, chewing gum)• Agree not to brush or floss teeth after 10:00 pm the night before and not eat or drink 4 hours before an appointment• Agree to the study instructions and visit schedule, including no eating or drinking for 4 hours before assessment appointments
--------------------------------------	---

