11.8 Sample Size

The sample size was estimated based on GI and PI scores from the preliminary data (CR 14-006) and from the FDA approval documents obtained under Freedom of Information for the predicate

device, Decapinol Oral Rinse, manufactured by Sinclair Pharmaceuticals (identical product now marketed as PerioShield Oral Health Rinse in the US by Sunstar Americas, Inc.)¹³

It is estimated that 34 subjects per group will provide 90% power to detect a difference of 0.40 (standard deviation (SD) of 0.5) in the GI and PI scores using a 1-sided 0.025 alpha level. To account for possible dropouts, a sample size of 50 subjects per group will be recruited.

It is anticipated that 200 subjects enrolled, with 50 subjects in each of the four groups will provide adequate power for the study endpoints. Subjects who drop out will not be replaced. Each subject will be asked to return to the study clinic around the middle of the two recalls (1.5 and 4.5 months) for study product replenishment, assessment of diaries, concomitant medications and reinforcement of product use instructions.

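### Does 90% power at 34 per group mislead, when success needs both the plaque and the gingival index?

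*SAP*

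**What the plan says.** SAP 6.1 states: "It is estimated that 34 subjects per group will provide 90% power to detect a difference of 0.40 (standard deviation of 0.5"), referring to the GI and PI scores, "using a 1-sided 0.025 alpha level". The protocol synopsis and protocol 11.8 give the same figures. Protocol 11.8 then moves from 34 to the recruited number: "To account for possible dropouts, a sample size of 50 subjects per group will be recruited". Its only statement about the power of the enrolled sample is "It is anticipated that 200 subjects enrolled, with 50 subjects in each of the four groups will provide adequate power for the study endpoints".

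The decision rule is in SAP 8.1 and, in the same terms, in protocol 11.3: "The study will be considered successful if both primary endpoints are met". The test for each endpoint is made "using an ANCOVA with treatment as the factor and baseline score as a covariate", comparing the 3M Oral Rinse with the vehicle control only. SAP 8.1 also says: "The level of significance will be two-sided alpha of 0.05". In the direction of benefit that is the same critical value as one-sided 0.025, so the sample size and the analysis agree on alpha.

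The documents do not give the power for winning on both endpoints, the correlation between PI and GI, an expected dropout rate, or whether the SD of 0.5 is before or after baseline adjustment.

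**The concern.** A trial that must win on two endpoints has less power than either test alone, unless the two test statistics are perfectly correlated. The calculation yields 34 from a single-endpoint test, while success is a joint event. A reader could take 90% as the chance of a successful trial with 34 evaluable per group. The same reader could take the step from 34 to 50 as room for 32% dropout, since (50 − 34)/50 = 0.32. On the stated inputs both readings are too favourable. If the enrolled number had been close to 34, the trial would have been under-sized for its own success rule.

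**Working it through.** **Inputs.** From SAP 6.1: difference 0.40, SD 0.5 (standardised effect 0.40/0.5 = 0.8), one-sided alpha 0.025, 34 per group, 50 recruited per group. From SAP 8.1: two groups in the comparison, both endpoints required. Assumed, because the documents give no value: the PI-GI correlation ρ, shown from 0 to 0.9.

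**Step 1: reproduce the plan's figure.** For one endpoint, power is the probability that a noncentral t variable with 2n − 2 degrees of freedom and noncentrality 0.8 × √(n/2) exceeds the central t critical value.

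- n = 33: noncentrality 3.250, critical value 1.998, power 89.3%.
- n = 34: noncentrality 3.298, critical value 1.997, power 90.15%.

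So 34 is exactly the smallest n that gives 90% for one endpoint. The arithmetic is correct.

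**Step 2: power for both endpoints.** At ρ = 0 this is the square of the single-endpoint power. At 34 per group: 0.9015² = 0.813. For ρ > 0 it is the bivariate normal probability with those marginals. Simulation of correlated t-tests agrees to within about 0.1 percentage point.

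| Evaluable per group | One endpoint | Both, ρ = 0 | Both, ρ = 0.5 | Both, ρ = 0.9 |
|---|---|---|---|---|
| 34 | 90.2% | 81.3% | 83.5% | 87.1% |
| 38 | 93.1% | 86.6% | 88.1% | 90.7% |
| 42 | 95.2% | 90.6% | 91.5% | 93.4% |
| 50 | 97.7% | 95.5% | 95.9% | 96.8% |

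**Step 3: the margin for loss.** The smallest n giving 90% for both is 42 at ρ = 0 (41 gives 89.7%) and 38 at ρ = 0.9 (37 gives 89.9%). Counting each lost subject as contributing nothing, 50 per group tolerates (50 − 42)/50 = 16% to (50 − 38)/50 = 24% loss while keeping 90% for both.

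**Step 4: the planned test is an ANCOVA.** If 0.5 is the raw SD and the correlation between baseline and 6-month score is r, the residual SD is 0.5 × √(1 − r²), with one further degree of freedom lost. The documents give no r, so it is assumed. The ranges below are for ρ from 0 to 0.9.

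- r = 0.3: power for both is 85.7% to 90.1% at 34, and 97.2% to 98.0% at 50.
- r = 0.5: power for both is 92.8% to 94.9% at 34.

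Power for both reaches 90% at 34 when r is about 0.43 (ρ = 0), or just under 0.30 (ρ = 0.9). If 0.5 is already the adjusted SD, the table in Step 2 applies unchanged.

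**Step 5: type I error.** Each endpoint is tested at its full level and both must succeed, so no alpha adjustment is needed and none is missing.

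**The case for a change.** The strongest case for a change is that the plan is sized for one event and judged on a harder one. If 32% of subjects were lost, the chance of missing success on the stated inputs would be about 13% to 19% rather than 10%. With no dropout rate, correlation or type of SD stated, a reader cannot see the true margin. The phrase about adequate power carries no number. The per-protocol analysis (SAP 5.3) drops subjects who miss either 6-month endpoint, so evaluable numbers matter there directly. A few words in three places would settle it.

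The omission stands: joint power is the natural figure to quote for two co-primary endpoints. The rest is weaker.

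- The documents claim power to detect a difference in the scores. They do not call 90% the probability of trial success.
- The 32% loss is inferred from 34 and 50. The plan does not predict it.
- The primary analysis is ITT, with missing PI and GI imputed within arm from baseline, 3-month and 6-month data (SAP 5.2 and 6.3). The study schedule and protocol 6.6 also provide for final assessments at discontinuation where possible. Imputation does not restore all the lost information, but a subject who drops out is not worth zero either, so 16% to 24% is a complete-case figure.
- Any shortfall at 34 depends on which SD was meant. Writing 81% to 87% into the plan without that condition could understate the power of the planned test.

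**Conclusion.** No change is needed. The 90% at 34 per group is a correct per-endpoint figure, and the protocol's claim that 50 per group is adequate also holds for the two-endpoint rule. On the stated inputs, power for both is at least 95.5% with 50 evaluable per group. It stays at or above 90% down to 42 evaluable even if PI and GI are uncorrelated. The 81% to 87% range arises only if as few as 34 per group contribute and 0.5 is the SD that applies in the analysis.

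These figures rest on the plan's difference of 0.40 and SD of 0.5 for both indices, and on an assumed PI-GI correlation of 0 to 0.9. Reporting the joint power would describe the design more fully, but it would leave the sample size, the ANCOVA, the success rule and the type I error as they are. This is a missing detail that a statistician can fill from the stated inputs, not a fault in the plan.

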6.2 Handling of Dropouts and Missing Data

Subjects with missing PI and/or GI data will be included in the ITT analysis using appropriate input data sets and imputation methods. It is assumed that the data will be multivariate normal and missing at random, and Expectation-Maximization (EM) algorithm will be used. If this assumption proves to be unreliable, other methods will be considered. In addition, a sensitivity analysis using alternative imputation methods to handle the missing data, namely last observation carried forward and using group means, will be conducted to examine the robustness of the primary analysis.

If a subject becomes pregnant during the study, the subject will be discontinued, and assessments completed.

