6.3 SAS Imputation Procedures

SAS PROC MI procedure will be used to perform imputations of the missing primary variables, namely, the PI and GI indices. The EM algorithm assumes multivariate normal distribution for the data; PI and GI values (baseline values included). The missing data for a given treatment group will be imputed independently with input data being the PI and GI data at all time points (baseline, 3 months and 6 months) from only that treatment group. The imputation procedure is valid when the missing data are missing at random. %MULTINORM macro can test for multivariate normality and PROC MI can display patterns of missing data.

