8.2.2 Baseline Visit

The clinical examinations will be conducted by calibrated examiners. The same examiner will perform the same clinical examination throughout the study. See Appendix 17.2 on training and calibration procedures of the clinical examiners. A subject blinding assessment question will be completed at the baseline visit after the first dose is taken. Professional cleaning by a dental hygienist will be completed at end of the baseline visit so all subjects start the study with a plaque free status.

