11.7 Missing Data

Subjects with missing PI and/or GI data will be included in the ITT analysis using appropriate input data sets and imputation methods. It is assumed that the data will be missing at random, and Expectation-Maximization (EM) algorithm will be used. If this assumption proves to be unreliable, other methods will be considered. In addition, a sensitivity analysis using alternative imputation methods to handle the missing data, namely last observation carried forward and using group means, will be conducted to examine the robustness of the primary analysis.

If a subject becomes pregnant during the study, the subject will be dropped and assessments completed.

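### The two named missing-data sensitivity analyses do not vary the missing-at-random assumption in a controlled way, and group-mean filling tends to confirm the primary result

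*SAP*

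**What the plan says.** The primary model in SAP 8.1 analyses "PI and GI scores at 6-months using an ANCOVA with treatment as the factor and baseline score as a covariate", in the ITT set, comparing 3M rinse with vehicle. On missing scores, SAP 6.2 states: "It is assumed that the data will be multivariate normal and missing at random, and Expectation-Maximization (EM) algorithm will be used". SAP 6.3 adds: "The missing data for a given treatment group will be imputed independently with input data being the PI and GI data at all time points", using data from that arm only. It names PROC MI but gives no number of imputations and no combining rule.

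Robustness is to be judged by two alternatives. SAP 6.2 gives them as "last observation carried forward and using group means, will be conducted to examine the robustness of the primary analysis", and protocol 11.7 agrees: "namely last observation carried forward and using group means". Neither document says whether a group mean is the mean of the subject's own arm or a pooled mean. Both allow for other methods if missing at random looks doubtful, but name no method and no trigger. No delta adjustment, reference-based imputation or tipping point appears.

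PI and GI are scored at baseline, 3 months and 6 months (protocol 5.1). The dental cleaning comes at the end of the baseline visit, "so all subjects start the study with a plaque free status" (protocol 8.2.2). Baseline scores therefore precede it, and eligible subjects score at least 1.0 on GI and 1.5 on PI (protocol 6.3).

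**The concern.** Observed data cannot show that missing at random fails. A sensitivity analysis therefore has to impose a known departure and show how large it must be before the conclusion changes. Group-mean filling imposes none: it supposes that dropouts average the same as completers in their arm, then counts the filled rows as real observations. LOCF does change the assumption, but the size and direction of the change depend on who left, when, and from which arm. The plan does not choose them. At stake is any statement in the final report that the PI and GI results are robust to missing data.

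**Working it through.** **The plan's own figure.** SAP 6.1 sizes the trial "to detect a difference of 0.40 (standard deviation of 0.5) in the GI and PI scores using a 1-sided 0.025 alpha level", with 90% power. The normal approximation gives n = 2 × (1.96 + 1.2816)² × 0.5² / 0.40² = 32.8, so 33 per group. With the noncentral t, power is 0.893 at 33 and 0.9015 at 34, so the stated 34 reproduces. Recruiting 50 leaves room to lose 50 − 34 = 16 per arm (32%).

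**Inputs.** From the documents: 50 per arm, ANCOVA on baseline, two-sided 0.05, SD 0.5, three scoring visits. Assumed, because the documents give no values: 5, 10 or 16 of 50 missing per arm, completely at random; correlation between visits 0.3 to 0.7; half of dropouts with no 3-month exam; a fall from baseline to 6 months of 0.5 or 1.0.

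**Group means (own arm).** With m observed out of n = 50, filled rows add nothing to the within-arm sum of squares but count in both n and the degrees of freedom. The ratio of reported to true standard error is r = √[(m − 1)/(n − 1) × m/n], and the two-sided type I error is 2 × [1 − Φ(1.96 r)].

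| Missing per arm | r | Error by formula | Error by simulation |
|---|---|---|---|
| 5 | √(44/49 × 45/50) = 0.899 | 7.8% | 7.5–8.3% |
| 10 | √(39/49 × 40/50) = 0.798 | 11.8% | 10.6–12.5% |
| 16 | √(33/49 × 34/50) = 0.677 | 18.5% | 17.2–19.9% |

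The simulations ran the two-arm ANCOVA under no true effect, over correlations 0.3 to 0.7. The same ANCOVA on observed 6-month scores alone rejected in 4.3–5.5% of runs. The standard error is understated by about 10%, 20% and 32%. Under a true difference of −0.40, the group-mean estimates averaged −0.399, −0.401 and −0.396, against −0.400, −0.399 and −0.394 from observed data. The estimate therefore does not move; only its apparent precision does.

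**LOCF, equal dropout.** Let a share d drop out of each arm, half of them with only a baseline score. Suppose the 3-month effect equals the 6-month effect. The expected estimate is then −0.40 × (1 − d/2), which is −0.38, −0.36 and −0.34 for d = 10%, 20% and 32% (simulated: −0.38, −0.36, −0.33). With no true effect, two-sided rejection was 1.7–5.0%, so there is no inflation.

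**LOCF, unequal dropout.** With 10% lost on the rinse and 30% on vehicle, 5% and 15% carry a baseline score to month 6. With no true effect, bias = (0.05 − 0.15) × fall, which is −0.05 for a fall of 0.5 and −0.10 for a fall of 1.0. Simulation gave the same biases, with false-benefit rates of 6.4% and 11.4% against a one-sided 2.5%. Reversing the dropout gives +0.05 and +0.10, against the rinse.

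**The case against.** Several points on the other side stand.

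- **LOCF and missing at random.** A reader might infer that neither method lets dropouts do worse than missing at random implies. That is wrong for LOCF. A pre-cleaning baseline score is worse than a missing-at-random prediction whenever scores fall after baseline, and under equal dropout LOCF shrank the effect without inflating error.
- **Reach of the baseline carry-forward.** A reader might infer that everyone lost before 3 months has a baseline score carried forward. The protocol's Study Schedule marks PI and GI at discontinuation as well as at 6 months, and protocol 6.6 asks for final assessments where feasible. Only subjects with no post-baseline exam are affected. How a discontinuation exam enters LOCF is not stated.
- **Comparison with the primary analysis.** A reader might infer that group-mean filling is less conservative than the analysis it checks. This is not shown. If the primary is one EM-filled data set, its error is nearly the same (7.9%, 11.0% and 18.1% at correlation 0.5). The inference would need a primary analysis that uses multiple imputation with combining rules, and SAP 6.3 does not settle that. If the primary is a single fill, the check shares the weakness it should expose.
- **Size.** No dropout rate is stated, and 16 of 50 is only the gap between 50 and 34. With 2 of 50 missing, the group-mean error is about 6%. False-benefit rates are roughly half the two-sided ones: about 4%, 5–6% and 9–11% against 2.5%. A pooled group mean would instead pull towards no difference. The LOCF biases are small beside 0.40 and rest on an assumed dropout imbalance.
- **Consequence.** Success is decided by the primary ITT analysis of both endpoints. The per-protocol set, which excludes subjects without 6-month scores, is a partial completer check, but it also removes non-compliers and is not the named sensitivity analysis.

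**Conclusion.** The point holds in a limited form. No pre-specified analysis varies missing at random in a controlled way. Own-arm group-mean filling adds no new assumption and understates the standard error. This result does not hinge on the assumed correlation, but its size depends on actual dropout and on the own-arm reading. LOCF is informative when early losses are balanced. Its bias can go either way when they are not, and the amount depends on the unknown fall from baseline.

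The documents do not support saying that the two analyses are worthless as a pair, or that the trial's success criterion is compromised by them. What is weak is the robustness claim they are meant to carry. Changing the plan is worthwhile because it is cheap.

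**What to change.** - **SAP 6.2 and protocol 11.7:** replace group-mean filling with a delta-adjusted tipping-point analysis for both PI and GI at 6 months, using multiple imputation with Rubin's combining rules. State the number of imputations and the range of delta. Report the delta at which either co-primary result loses significance.
- **Optional addition:** reference-based imputation, in which missing 3M scores are drawn from the vehicle-arm distribution.
- **SAP 6.3:** if that addition is made, state that the within-arm-only imputation rule does not apply to it; otherwise the two sections conflict.
- **LOCF:** it may stay, labelled as supplementary. Say how discontinuation exams are used, and report by arm how many subjects have a baseline score carried forward.

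The cost is SAP and protocol wording plus modest programming in PROC MI, which SAP 6.3 already names. The sensitivity results will look less favourable than those from single fills.
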